4.2.5 Dose Modifications

Intra-patient dose reduction to 1.2 mg/kg will be allowed depending on the type and severity of toxicity. **Table 1** describes the recommended dose modifications for study treatment-associated toxicity (toxicity with suspected relationship to SGN-35).

Peripheral Neuropathy: Peripheral neuropathy should be managed using a combination of dose delay and reduction to 1.2 mg/kg. For new or worsening Grade 2 or 3 neuropathy, dosing should be held until neuropathy improves to Grade 1 or baseline and then restarted at 1.2 mg/kg. For Grade 4 peripheral neuropathy, SGN-35 should be discontinued.

A study of brentuximab vedotin (SGN-35) in CD30-positive systemic mastocytosis with or without an associated hematological clonal non-mast cell lineage disease (AHNMD)

Neutropenia: Neutropenia should be managed by dose delays and reductions. The dose of SGN-35 should be held for Grade 3 or 4 neutropenia until resolution to baseline or Grade 2 or lower. Growth factor support should be considered for subsequent cycles in patients who experience Grade 3 or 4 neutropenia. In patients with recurrent Grade 4 neutropenia despite the use of growth factors, discontinuation or dose reduction of SGN-35 to 1.2 mg/kg may be considered.

Acute Pancreatitis: Acute pancreatitis has been identified as an important potential risk associated with brentuximab vedotin dosing. Dosing should be held until a diagnosis of acute pancreatitis has been excluded if clinically suspected.

The start of the next cycle may be delayed for up to 30 days if additional time is required for the patient to recover from study treatment-associated toxicity experienced during the current cycle (**Table 1**). Delays of greater than 30 days are prohibited without approval of the Principal Investigator of the entire study, [name].

Doses reduced for treatment-related toxicity should not be re-escalated.

If 4 out of the 11 patients experience emergent drug-related Grade 3 or 4 non-hematologic toxicity, the study will be placed on hold for safety review, and if restarted upon study amendment, the starting dose of therapy for subsequent patients would be no more than 1.2 mg/kg.

Table 1. Dose Reduction Algorithms for Non-Hematologic and Hematologic Toxicity With Suspected Relationship to SGN-35

Toxicity	Grade 1	Grade 2	Grade 3	Grade 4

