Non-Hematologic	Continue at same dose level.	
Continue at same dose level, except in the event of Grade 2 neuropathy.
 
For Grade 2 neuropathy, withhold dose until toxicity is \leq Grade 1 or has returned to baseline, then reduce the dose to 1.2 mg/kg and resume treatment.
 
If Grade 2 neuropathy recurs at a dose of 1.2 mg/kg, the patient should be discontinued from study.
	
Withhold dose until toxicity is \leq Grade 1 or has returned to baseline, then resume treatment at the same dose level. ^a
 
If the toxicity has not returned to \leq Grade 1 after holding the dose for 30 days, then the patient should be discontinued from the study.
 
If the same Grade 3 toxicity recurs, withhold dose until toxicity is \leq Grade 1 or has returned to baseline, then reduce to the 1.2 mg/kg/level. ^a
 
For patients with recurrence of the same Grade 3 toxicity, the patient should be discontinued from the study.
 
For Grade 3 neuropathy, withhold dose until toxicity is \leq Grade 1 or has returned to baseline, then reduce the dose to 1.2 mg/kg and resume treatment.
 
If Grade 3 neuropathy recurs at a dose of 1.2 mg/kg, the patient should be discontinued from study.
	
Withhold dose until toxicity is \leq Grade 1 or has returned to baseline, then reduce dose to 1.2 mg/kg and resume treatment. ^a
 
If the toxicity has not returned to \leq Grade 1 after holding the dose for 30 days, then the patient should be discontinued from the study
 
For patients with recurrence of the same Grade 4 toxicity at a dose of 1.2 mg/kg, the patient should be discontinued from the study
 
For Grade 4 neuropathy, SGN-35 should be discontinued.

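### For a patient already at 1.2 mg/kg, the neuropathy paragraph of section 4.2.5 and Table 1 disagree on recurrence, and Table 1 does not clearly cover a higher-grade or first neuropathy

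*Combined protocol and SAP*

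**What the plan says.** The peripheral neuropathy paragraph of section 4.2.5 begins: "For new or worsening Grade 2 or 3 neuropathy, dosing should be held". The action is that "dosing should be held until neuropathy improves to Grade 1 or baseline and then restarted at 1.2 mg/kg". Its only stopping instruction is: "For Grade 4 peripheral neuropathy, SGN-35 should be discontinued". It makes no exception for recurrence or for a patient already on the lower dose.

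Table 1, in the same section, treats Grade 2 and Grade 3 neuropathy in separate cells. Both hold the drug until recovery, "then reduce the dose to 1.2 mg/kg and resume treatment". Each cell then adds its own stop. Grade 2 cell: "If Grade 2 neuropathy recurs at a dose of 1.2 mg/kg, the patient should be discontinued from study". Grade 3 cell: "If Grade 3 neuropathy recurs at a dose of 1.2 mg/kg, the patient should be discontinued from study".

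Three other provisions bear on the reading:

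- Section 4.2.2 directs treatment-associated Grade 2 peripheral neuropathy to Table 1. It does not mention Grade 3.
- Section 4.2.5 also states: "Doses reduced for treatment-related toxicity should not be re-escalated".
- The Grade 3 cell removes from the study a patient whose toxicity has not come down to Grade 1 or less after a 30-day hold. Section 4.2.5 bars delays beyond 30 days unless the overall Principal Investigator approves.

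**The concern.** Two parts of one section appear to send the same patient in different directions, back onto drug or out of the study. Neuropathy is where this matters most: section 1.2 reports peripheral sensory neuropathy in 44% of patients in the two phase 2 lymphoma studies, the highest figure listed. Section 8.1.1 describes a main site and a sub-site, so the instruction may be read by more than one team.

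There is also a data consequence. For a patient who discontinues early, section 4.3 provides for adverse-event follow-up (if the cause is drug-related) and survival follow-up every 6 months, but no continued response visits. A response has to be confirmed at 84 days or later (section 4.7.1), and the first stage turns on 2 responders of 11 (section 7.8). Whether a patient leaves the study can therefore bear on whether a response is confirmed.

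**Working it through.** The plan states no figure to reproduce here, so the check sets the passages side by side.

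**Step 1: is a recurrence also a worsening?** Section 3.3.2 excludes Grade 2 or higher neuropathy at entry, so baseline is Grade 0 or 1. The paragraph and both table cells allow dosing to resume only at Grade 1 or less, or at baseline. A patient who has resumed is therefore at Grade 1 at most, and any later Grade 2 or 3 is a worsening. The paragraph's wording covers it.

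**Step 2: is the patient still at 1.2 mg/kg?** Yes, because reduced doses are not raised again.

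**Step 3: trace each event in a patient at 1.2 mg/kg.**

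| Event | Neuropathy paragraph | Table 1 | Result |
|---|---|---|---|
| Grade 2 again, after reduction for Grade 2 | Hold, restart at 1.2 mg/kg | Discontinue from study | Disagree; section 4.2.2 points to the table |
| Grade 3 again, after reduction for Grade 3 | Hold, restart at 1.2 mg/kg | Discontinue from study | Disagree; no specific pointer |
| First Grade 3, after reduction for Grade 2 | Hold, restart at 1.2 mg/kg | Literally: hold, reduce to 1.2 mg/kg, resume | Agree on the literal reading, but the reduction cannot be carried out |
| First Grade 2 or 3 neuropathy, at 1.2 mg/kg for another toxicity | Hold, restart at 1.2 mg/kg | Literally: hold, reduce to 1.2 mg/kg, resume | As above |
| Grade 4 | Stop SGN-35 | Stop SGN-35 | Agree |

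The fourth row can arise because Table 1 also reduces to 1.2 mg/kg for other non-hematologic Grade 4 events, repeated Grade 3 events and electrolyte abnormalities.

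**Step 4: how many readings does the third row allow?** Three. The line "For Grade 3 neuropathy, withhold dose until toxicity is" and what follows can be applied as written. The cell can be taken as silent, since it seems to presuppose a patient at 1.8 mg/kg. Or the Grade 3 event can be counted as the earlier neuropathy recurring, which leads to discontinuation. The general Grade 3 lines do not settle it, because they too depend on the same Grade 3 toxicity recurring.

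**Step 5: size.** Applied to this trial, 44% gives 0.44 × 11 = 4.84 patients in the first stage and 0.44 × 26 = 11.44 over both. These are all grades, from other diseases. To meet the recurrence or higher-grade rows, a patient needs a Grade 2 or 3 event that leads to reduction and then a second event at 1.2 mg/kg. Neither probability is in the documents.

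Purely as an illustration of how loose the answer is, assume that 25–50% of the 44% reach Grade 2 or more, and that 20–50% of those have a second event:

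- Reduced to 1.2 mg/kg: 0.44 × 0.25 = 0.11 to 0.44 × 0.50 = 0.22 per patient.
- Second event: 0.11 × 0.20 = 0.022 to 0.22 × 0.50 = 0.11 per patient.
- At least one among 11: 1 − 0.978^11 = 0.22 to 1 − 0.89^11 = 0.72.
- Expected number among 11: 0.24 to 1.21.

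Both assumed ranges are mine, and the width of the result shows that it is not an estimate.

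**The case against.** The best defence is that Table 1 governs. Section 4.2.2 sends Grade 2 neuropathy there, section 4.2.5 introduces the table before the paragraph, and the paragraph never mentions recurrence, so it may be only a summary of the first event. This has force for Grade 2. For Grade 3 there is only the general introduction, which presents the table as recommended and does not say that it overrides the text. Ranking the table first would also leave its own gap open.

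A second defence is that the first-Grade-3 case is a gap and not a contradiction. That is right. A reader might infer that Table 1 positively orders re-dosing after the worse event while removing a patient for the milder one. The documents do not support that as the plan's rule: it follows only from a literal reading of a step that cannot be carried out at 1.2 mg/kg. Re-dosing after Grade 3 is also subject to the 30-day limit on holds.

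A reader might also cite patients started at no more than 1.2 mg/kg after the safety hold triggered by 4 of 11 patients. Restart there already requires an amendment, so those patients would be treated under text not yet written.

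**Conclusion.** The neuropathy instructions need reconciling. On recurrence at 1.2 mg/kg the paragraph and the table conflict; the conflict is softened for Grade 2 by section 4.2.2 and unranked for Grade 3. For a higher-grade return or a first neuropathy at 1.2 mg/kg, Table 1 is unclear and open to more than one reading. This second limb rests on literal wording and is the weaker of the two.

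The number of patients affected cannot be computed from the documents. A reader might take the assumed 25–50% share of Grade 2 or more and obtain 1 − 0.89^11 = 0.72 to 1 − 0.78^11 = 0.93. That is the chance of at least one first dose reduction among 11 patients, on an undocumented share, and not the chance of meeting the conflict.

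Nor do the documents show that the first-stage decision would change. Table 2 calls for marrow and imaging at end of treatment if that comes before cycle 8, and neither the size nor the direction of any effect on 2 of 11 can be derived. An effect on an individual patient's confirmed response is possible, and no more than that is claimed.

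**What to change.** Amend the peripheral neuropathy paragraph of section 4.2.5 and the Grade 2 and Grade 3 neuropathy entries of Table 1 so that they carry one consistent instruction, and align the cross-reference in section 4.2.2 with it for both grades. The text should state what applies to a patient already at 1.2 mg/kg in three situations: neuropathy recurs at the same grade; it returns at a higher grade than the one that led to the reduction; or it appears for the first time. What the instruction should be in each situation is a clinical decision for the sponsor, and none is proposed here. The cost is amendment wording, with no added procedures or patients.

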3.3.2 Inclusion and exclusion criteria

Inclusion criteria

- Aged ≥ 18 years of age
- Patient must give written informed consent
- ECOG performance status of 0-3 (Appendix A)
- Life expectancy > 12 weeks
- Meeting the following laboratory values:
 - AST and ALT ≤ 2.5 x Upper Limit of Normal (ULN) (Exception: ≤ 5 x ULN, if elevation is considered related to ASM/MCL)
 - Serum direct bilirubin ≤ 1.5 x ULN; if considered related to ASM/MCL ≤ 3 x ULN
 - Serum creatinine ≤ 2.0 mg/dL
 - Creatinine clearance (CrCl) ≥ 30 mL/min
- A diagnosis of SM per 2008 WHO Criteria (see Appendix B)
- Neoplastic mast cells must express CD30 by immunohistochemistry or flow cytometry (histopathologic determination made centrally by [name])
- Patients with ASM and MCL (diagnostic criteria in Appendix C) with or without an AHNMD are required to have at least one of the eligible organ damage findings as defined by the international consensus response criteria
- Both females of childbearing potential and males who have partners of childbearing potential must agree to use an effective contraceptive method during the study and for 30 days following the last dose of study drug.
- Females of childbearing potential must have a negative serum or urine B-hCG pregnancy test result within 7 days prior to the first dose of SGN-35. Females of non-childbearing

potential are those who are postmenopausal greater than 1 year or who have had a bilateral tubal ligation or hysterectomy.

Exclusion criteria

- Patients unwilling or unable to comply with the protocol.
- Any other concurrent severe known disease (except carcinoma in-situ) concurrent severe and/or uncontrolled medical condition (eg, uncontrolled diabetes, or active uncontrolled infection) which could compromise participation in the study.
- History of another primary malignancy that has not been in remission for at least 3 years. (The following are exempt from the 3-year limit: non-melanoma skin cancer, fully excised melanoma in situ [Stage 0], curatively treated localized prostate cancer, and cervical carcinoma in situ on biopsy or a squamous intraepithelial lesion on PAP smear.)
- Patients with cardiovascular disease including congestive heart failure Grade 3 or 4 according to the NYHA classification, left ventricular ejection fraction of < 50%, myocardial infarction within previous 6 months and poorly controlled hypertension.
- Women who are pregnant or lactating.
- Patients with \geq Grade 2 neuropathy

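### Table 1 lets a patient who is back at a Grade 2 or worse baseline resume dosing, while its 30-day rule removes the same patient

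*Combined protocol and SAP*

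**What the plan says.** All of this is in the combined protocol and SAP.

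- **Resume rule, Grade 3 non-hematologic (section 4.2.5, Table 1).** Dosing is held until toxicity is Grade 1 or lower "or has returned to baseline, then resume treatment at the same dose level".
- **Resume rule, Grade 4 non-hematologic (same table).** Dosing is held until toxicity is Grade 1 or lower "or has returned to baseline, then reduce dose to 1.2 mg/kg and resume treatment".
- **30-day rule, in both cells.** The patient is removed if toxicity has not come down to at most "Grade 1 after holding the dose for 30 days, then the patient should be discontinued from the study". Baseline is not mentioned.
- **Cap on delay (section 4.2.5, text).** The next cycle may be put back by up to 30 days. "Delays of greater than 30 days are prohibited without approval of the Principal Investigator of the entire study".
- **Recovery rules elsewhere in section 4.2.5.** For neuropathy, "dosing should be held until neuropathy improves to Grade 1 or baseline". For Grade 3 or 4 neutropenia, dosing is held "until resolution to baseline or Grade 2 or lower".
- **Entry (section 3.3.2).** Patients are "required to have at least one of the eligible organ damage findings as defined by the international consensus response criteria". Appendix G, Table 3 lists those findings. Patients at or above "Grade 2 neuropathy" are excluded.

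**The concern.** The two rules in each cell use different definitions of recovery. For a patient who entered with normal or Grade 1 values the difference has no effect. For a patient who entered with Grade 2 or worse disease-related damage in the affected organ, the 30-day rule asks for a value better than the one at entry. That is a test of disease improvement, not of recovery from the drug.

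This trial recruits patients with organ damage, so a baseline above Grade 1 is part of the intended population. Two investigators, or two sites, could treat identical patients in opposite ways, each following a sentence in the table. The patient stands to lose the remaining cycles.

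Follow-up is largely kept after removal. Still applying are:

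- weekly follow-up for four weeks, or until the event resolves or stabilizes if sooner, and survival contact (section 4.3);
- end-of-treatment marrow and imaging, and the day +30 visit for non-responders (Table 2, notes e to g);
- imaging, if feasible, on removal before the end of cycle 4 (section 4.8.1);
- follow-up of unresolved adverse events (section 8.1).

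**Working it through.** The plan gives no figure on this point, so the check is a comparison of the two rules by baseline grade.

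**Definitions**

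- R (resume) is true if the current grade is ≤ 1 or the toxicity is back at baseline.
- D (discontinue) is true if the current grade is > 1 after a 30-day hold.

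| Baseline grade | Grade when the hold reaches 30 days | R | D |
|---|---|---|---|
| 0–1 | ≤ 1 | true | false |
| 0–1 | ≥ 2 | false | true |
| 2 | ≤ 1 | true | false |
| 2 | 2 (after a Grade 3 or 4 event) | **true** | **true** |
| 2 | 3 or 4 | false | true |
| 3 | 3 (after a Grade 4 event) | **true** | **true** |

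R and D hold together only when baseline is Grade 2 or worse and the patient is back at that baseline.

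**Can such a patient enrol?** Appendix G, Table 3 lists 4 non-hematologic + 5 hematologic = 9 eligible findings. Of the 4 non-hematologic ones, splenomegaly carries no stated grade, which leaves 4 − 1 = 3 with a stated grade of 2 or worse: ascites or pleural effusion, liver function tests, and albumin. Section 3.3.2 admits disease-related AST and ALT up to 5 × ULN and direct bilirubin up to 3 × ULN, and sets no limit on albumin.

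**Example.** Albumin is 2.5 g/dL at entry (Appendix G puts Grade 2 or worse below 3.0 g/dL). A drug-related Grade 3 fall follows, and albumin is 2.5 g/dL again when the hold reaches 30 days. The patient is at baseline, so R is true. The grade is above 1, so D is true.

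**Is the omission systematic?** The non-hematologic row uses the returned-to-baseline clause 5 times. Two are for neuropathy, leaving 5 − 2 = 3 general recovery tests (Grade 3 first event, Grade 3 recurrence, Grade 4), and all 3 accept baseline. Neither of the 2 thirty-day tests does.

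**Does anything else settle it?** Footnote a covers electrolyte abnormalities and footnote b covers lymphopenia. The adjustment for abnormal baseline counts stands only in the hematologic row. The approval rule for delays beyond 30 days does not say what counts as recovery.

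**Where the overlap stops**

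- Neuropathy: Grade 2 or worse is excluded at entry, so baseline is always ≤ Grade 1.
- Hematologic toxicity: it has its own row, without the 30-day sentence.
- Recovery found before day 30: the resume sentence ends the hold and D is never reached.
- Beyond day 30: it arises only if the overall Principal Investigator approves a longer hold.

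**Could recovery first be documented that late?** Yes. In cycles 2–8 scheduled chemistry falls on Day 1 only, and Day 10 covers hematology and adverse events (sections 4.6.1 and 4.8.1). The weekly-laboratory instruction in Table 1 is in the hematologic row. No retest interval is set for a non-hematologic hold.

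**Cycles lost.** With 8 planned cycles (section 3.2) and removal during the hold after cycle k, the loss is 8 − k. For k = 1 to 7 this runs from 7 down to 1.

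**The case against.** The strongest counter-argument is that Table 1 concerns only toxicity suspected to be related to the drug. Once albumin is back at its entry value the drug effect has gone; what remains is disease, and the 30-day sentence has nothing to act on. This is probably close to the intent, but it does not rescue the text. If toxicity already excluded baseline disease, the baseline clause in the resume sentences would be redundant.

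A second argument reads each cell in order: hold until recovered by either route, then resume; stop if not recovered by 30 days. On this view the 30-day sentence is meant for patients who entered at Grade 1 or lower. Nothing in the sentence limits it to them.

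Third, Table 1 is described as recommended, and the overall Principal Investigator rules on longer delays. That leaves room for judgement, but it does not say which sentence governs at day 30, and discretion is how like patients come to be treated differently.

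Fourth, a stricter test after a long hold can be a defensible safety choice in patients with existing organ damage. That stands as a possibility; if it was intended, the plan should say so.

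It also stands that the overlap is narrow, that the protocol names no formal assessment at day 30, and that the count of 1 to 7 lost cycles would follow from any removal and does not measure how often this one occurs.

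**Conclusion.** The point holds: Table 1 is wrong as written, and the matter is minor. In the Grade 3 and Grade 4 non-hematologic cells, a patient who is back at a Grade 2 or worse baseline when the hold reaches 30 days satisfies both the rule to resume and the rule to remove, and no other text decides between them.

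The conclusion assumes that grade means the observed grade of the affected parameter, and that recovery to baseline is found as the hold reaches 30 days or during an approved longer hold. The documents do not allow the number of such patients to be estimated. No sample size, error rate or response-rate figure depends on the point. The consequence is for the individual patient and for consistency between investigators.

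**What to change.** In both cells, put the baseline alternative into the 30-day sentence and refer to the approved extension. For example: *A patient whose toxicity is neither Grade 1 or lower nor back at baseline once dosing has been held for 30 days (or for a longer delay approved by the overall Principal Investigator) is to be discontinued from the study.*

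If the stricter limit is deliberate, keep it and add that it overrides the resume sentence for patients whose baseline is above Grade 1.

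The cost is two sentences in Table 1. The change matches the resume sentences in the same cells and the recovery rules that section 4.2.5 already uses for neuropathy and neutropenia. It adds no visits or procedures.

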Hematologic	Continue at same dose level.	Continue at same dose level.	
 The dose of SGN-35 should be held for Grade 3 or 4 neutropenia until resolution to baseline or Grade 2 or lower. Growth factor support should be considered for subsequent cycles in patients who experience Grade 3 or 4 neutropenia. In patients with recurrent Grade 4 neutropenia despite the use of growth factors, discontinuation or dose reduction of SGN-35 to 1.2 mg/kg may be considered. Dose interruption for anemia will not be undertaken. If patients have Grade 2 to 3 of these events at baseline only Grade 4 cytopenias suspected to be related to study drug will be considered as hematologic toxicity. ^b Obtain weekly labs until lab returns to baseline or Grade 2. G-CSF for treatment of neutropenic fever may be used, but not for treatment of neutropenia alone, nor for infection prophylaxis in the setting of neutropenia. 	

^a Patients who develop emergent Grade 3 or 4 electrolyte laboratory abnormalities will have the dose of SGN-35 reduced to 1.2 mg/kg in subsequent cycles. If the same Grade 3 or 4 electrolyte abnormalities re-occur, SGN-35 will be discontinued.

^b Patients who develop Grade 3 or 4 lymphopenia may continue study treatment without interruption.

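### Table 1 tells sites both to reduce the dose and to stop treatment when the same Grade 3 non-hematologic toxicity recurs, because neither line names a dose

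*Combined protocol and SAP*

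**What the plan says.** The starting dose is 1.8 mg/kg (Section 4.2.2), the only reduced level is 1.2 mg/kg, and a dose reduced for treatment-related toxicity is not raised again (Section 4.2.5). For non-hematologic Grade 3 toxicity in general, Table 1 gives these steps:

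- **First event:** hold until Grade 1 or lower, or until the toxicity "has returned to baseline, then resume treatment at the same dose level".
- **Recurrence, reduction line:** "If the same Grade 3 toxicity recurs, withhold dose until toxicity is" Grade 1 or lower, or "has returned to baseline, then reduce to the 1.2 mg/kg/level".
- **Recurrence, discontinuation line:** "For patients with recurrence of the same Grade 3 toxicity, the patient should be discontinued from the study".

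The same row of the table has three other lines that stop treatment on recurrence, and each names the dose:

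- **Grade 2 neuropathy:** "If Grade 2 neuropathy recurs at a dose of 1.2 mg/kg, the patient should be discontinued from study".
- **Grade 3 neuropathy:** "If Grade 3 neuropathy recurs at a dose of 1.2 mg/kg, the patient should be discontinued from study".
- **Grade 4:** the stop applies "For patients with recurrence of the same Grade 4 toxicity at a dose of 1.2 mg/kg".

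Electrolyte abnormalities have a separate rule in footnote a: reduce to 1.2 mg/kg after the first event, and then "If the same Grade 3 or 4 electrolyte abnormalities re-occur, SGN-35 will be discontinued".

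**The concern.** The reduction line and the discontinuation line are triggered by the same event, and neither says at which dose it applies. A patient who resumed at 1.8 mg/kg and has a first recurrence meets both. Following one line means breaking the other.

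This is an operative dosing rule in a study with more than one site (Sections 8.1.1 and 8.2.2). On the literal text, a patient can be taken off treatment at a point where a reduction was probably meant, and two sites can handle the same event differently. What is at stake is patient management and treatment exposure.

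**Working it through.** No stated figure has to be reproduced here. The check compares the rules line by line and then works out the exposure at stake.

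**1. Where dose qualifiers appear.** The cells of the non-hematologic row contain four lines that stop treatment on recurrence.

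| Rule | Action after first event | Dose named in the stop line? |
|---|---|---|
| Grade 2 neuropathy | reduce to 1.2 mg/kg | yes, 1.2 mg/kg |
| Grade 3 neuropathy | reduce to 1.2 mg/kg | yes, 1.2 mg/kg |
| Grade 4, other than neuropathy | reduce to 1.2 mg/kg | yes, 1.2 mg/kg |
| Grade 3, general | resume at same dose | no |

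Three of the four name the dose. If footnote a is added as a fifth line, it is three of five. The one cell rule without the qualifier is also the only one that returns the patient to the unchanged dose after the first event. Under the other rules, and under footnote a, the patient has already been reduced by the time the toxicity comes back. Under the general Grade 3 rule the patient normally has not, so this is where the qualifier is most needed.

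**2. Whether another passage supplies it.** The text of Section 4.2.5 covers neuropathy, neutropenia and pancreatitis. Footnote a covers electrolytes only. Neither addresses recurrence of other Grade 3 toxicity.

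**3. Which lines a recurrence meets, by dose at the time.**

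| Wording | Recurrence at 1.8 mg/kg | Recurrence at 1.2 mg/kg |
|---|---|---|
| As written | both lines | both lines |
| Dose added to discontinuation line only | reduction only | both lines |
| Dose added to both lines | reduction only | discontinuation only |

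**4. Exposure at stake.** Inputs are 8 planned cycles with one dose each (Sections 3.2 and 4.2.2), a full dose of 1.8 mg/kg and a reduced dose of 1.2 mg/kg. Suppose the first recurrence follows dose k at 1.8 mg/kg. The earliest case is k = 2, because the table resumes treatment after the first event.

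- Literal stop: total dose = 1.8k mg/kg.
- Stepwise reading, maximum: total dose = 1.8k + 1.2(8 − k) mg/kg.
- Doses forgone by the literal stop: up to 8 − k.

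| k | Literal stop (mg/kg) | Stepwise maximum (mg/kg) | Doses forgone, up to |
|---|---|---|---|
| 2 | 1.8 × 2 = 3.6 | 3.6 + 1.2 × 6 = 10.8 | 6 |
| 4 | 1.8 × 4 = 7.2 | 7.2 + 1.2 × 4 = 12.0 | 4 |
| 7 | 1.8 × 7 = 12.6 | 12.6 + 1.2 × 1 = 13.8 | 1 |
| 8 | 1.8 × 8 = 14.4 | 14.4 + 0 = 14.4 | 0 |

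These are upper limits for the initial 8 cycles. They assume that the patient recovers enough to be re-dosed and has no later reason to stop.

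**The case against.** The strongest reply is that this is a missing qualifier whose meaning can be recovered. The lines run in order, and if the last one governed a first recurrence, the reduction line above it would never operate. Resume, reduce, stop is the only reading that gives every line effect, and the neighbouring rules follow the same pattern. Footnote a also names no dose in its stop sentence, yet its order makes the meaning clear. The table is described as recommended. The misreading errs towards stopping drug after repeated toxicity, so it does not produce unsafe dosing. The patient stays in the primary efficacy population (Section 7.1) and is followed for survival (Section 4.3). The scope is narrow, in a first stage of 11 patients.

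Much of this stands. The intended sequence can probably be inferred, the number of patients affected may be small, and the safety direction is conservative. But the comparison with footnote a does not carry over: that rule reduces at the first event, so order settles its meaning, whereas the general Grade 3 rule resumes at full dose. Nor do the two recurrence lines contain any word marking a second recurrence or a prior reduction. A careful reader who sees the dose named elsewhere in the row could take its absence here as deliberate.

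A second objection is that qualifying the discontinuation line alone would do, because a patient already at 1.2 mg/kg cannot be reduced to it. That is enough for a patient who starts at 1.8 mg/kg and has no other reduction. A patient earlier reduced for, say, neuropathy would still meet both lines, one telling the site to hold and treat at 1.2 mg/kg and the other to stop. The same would hold for patients started at 1.2 mg/kg after a safety hold. That restart needs an amendment anyway, so it is the weaker example.

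**Conclusion.** The concern holds. For a recurrence of the same Grade 3 non-hematologic toxicity, other than neuropathy or an electrolyte abnormality, Table 1 as written requires both reduction and discontinuation. At 1.8 mg/kg, the discontinuation line very probably gives the action that was not intended.

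Per affected patient, the exposure lost ranges from none to at most 6 of 8 doses, on the assumptions of recovery and no later stop. The documents give no Grade 3 recurrence rate, so the number of patients cannot be estimated. The effect on the response rate cannot be quantified, and the Section 7.8 error rates and stopping boundaries are unaffected. The rule should be corrected because it governs dosing and the correction is nearly free.

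**What to change.** Add a dose condition to each of the two lines in the Grade 3 non-hematologic cell:

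- **Reduction line:** make it apply when the same Grade 3 toxicity recurs *at 1.8 mg/kg*. The action stays the same: hold to Grade 1 or lower or to baseline, then reduce to 1.2 mg/kg.
- **Discontinuation line:** make it apply when the same Grade 3 toxicity recurs *at a dose of 1.2 mg/kg*.

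Each recurrence then leads to one action, in line with the Grade 4 and neuropathy rules. One consequence should be confirmed as intended: a patient already at 1.2 mg/kg for another reason would stop at the first recurrence, since the protocol defines no lower dose.

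The cost is a clarifying amendment to two lines of one table cell. Sample size, visits and analysis do not change.
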